### **Objectives**

The primary objective of this study is to assess the acute changes in peripapillary and macular blood flow after an intake of oral caffeine in glaucoma patients and healthy subjects, by using optical coherence tomography angiography (OCTA).

### **Hypothesis**

Ingestion of caffeine in glaucoma patients and healthy subjects may decrease peripapillary and macular blood flow.

### **Background and Significance**

Caffeine is the most widely consumed drinking nutrient in the world; it is naturally included in coffee, tea and cocoa beans. Although caffeine is naturally or synthetically found in many dietary sources (energy drinks, soda-type beverages, juice, chewing gums, candy, etc.), it is mostly linked to coffee consumption since it is the most commonly ingested beverage worldwide. Daily consumption of coffee varies among nations, for example, an average daily intake of caffeine of about 180 mg/day is reported in the United States, and 260 mg/day in Japan. It is known that a regular cup of coffee (236 mL) contains approximately 135 – 150 mg of caffeine and a daily intake of about 200 mg/day is considered moderate.

Caffeine works by binding to adenosine receptors of the central and peripheral nervous systems, heart and blood vessels. It affects various organs and its effect on the vascular system can be explained by two possible mechanisms: binding to the vascular smooth muscle receptors and leading to vasoconstriction or increasing the intracellular calcium concentration which leads to increased nitric oxide synthesis and vasodilatation. It decreases ocular blood flow due to vasoconstriction. In a recent study, a significantly decrease in choroidal thickness after 200 mg oral caffeine intake was observed. In other studies, decrease in retinal blood flow in healthy volunteers was demonstrated by using blue field simulation technique, laser speckle tissue circulation analyzer and OCTA.

Optical coherence tomography angiography (OCTA) is a novel imaging tool that separates moving scatters from static background tissue to create three-dimensional angiograms by assessing the change in the OCT signal caused by flowing blood cells. This new technology enables a fast and non-invasive angiogram scan. Numerous studies have validated the use of the OCTA in the evaluation of various diseases of the retina, choroid, and optic nerve by evaluation of the total blood flow and microvasculature structure.

The correlation of IOP changes after caffeine intake was evaluated and a transient increase in IOP of approximately 1 - 2 mmHg within two hours were reported in previous studies. Although an associated transient IOP elevation has been reported with caffeine, it is not considered as a risk factor for glaucoma. In the present study, we aim to evaluate the optic nerve head and macular blood flow changes by using OCTA in glaucoma patients at different stages and healthy subjects before and after ingestion of 200 mg caffeine tablet.

## **Methods:**

### **Study Design**

Interventional Prospective Clinical Trial

### **Inclusion and Exclusion Criteria**

#### **Inclusion criteria:**

Age 18-90

- Glaucoma patients
- Healthy subjects

#### **Exclusion Criteria:**

- Diseases, ophthalmic or systemic, that are likely to affect the OCTA test results.
- More than moderate grade cataract
- Nystagmus
- Inability to fixate for OCTA scan
- Macular degeneration other than mild drusen or pigmentary changes
- Diabetic retinopathy
- Neovascular glaucoma

- Current macular edema
- Prior laser treatment to the retina
- Inflammatory retinopathy or choroidopathy
- Keratoconus or other corneal ectasia
- Corneal scarring in central 4 mm
- Non-glaucoma optic neuropathies: ischemic and traumatic optic neuropathy, optic atrophy
- Rheumatologic diseases with vascular involvement: rheumatoid arthritis, systemic lupus erythematosus,
- Raynaud's phenomena
- Pregnant and lactating women
- Patients with mental illness (schizophrenia, bipolar disorder, anxiety symptoms)
- Alcohol addiction
- Pre-existing bladder symptoms
- Pre-existing cardiac disease
- Pre-existing sleep disorder
- Refractive spherical diopter >5 or cylinder > 3.
- Subjects who would develop a possible tolerance to caffeine (subjects drinking more than one cup of coffee per day)

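### The caffeine-tolerance exclusion tests only for coffee, so regular users of other caffeine sources can be enrolled, and any tolerance they have would pull the acute blood-flow change toward zero

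*Protocol*

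**What the plan says.** The relevant item in the Protocol's Exclusion Criteria reads "Subjects who would develop a possible tolerance to caffeine (subjects drinking more than one cup of coffee per day". The bracket is the only operational definition of tolerance in the document.

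The Background and Significance section takes a wider view of exposure. It says of caffeine that "it is naturally included in coffee, tea and cocoa beans", and then that "caffeine is naturally or synthetically found in many dietary sources (energy drinks, soda-type beverages, juice, chewing gums, candy, etc". The same sentence goes on to say that "it is mostly linked to coffee consumption since it is the most commonly ingested beverage worldwide". For quantities, it states that "a regular cup of coffee (236 mL) contains approximately 135 – 150 mg of caffeine" and that "an average daily intake of caffeine of about 180 mg/day is reported in the United States".

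The primary objective is to "assess the acute changes in peripapillary and macular blood flow after an intake of oral caffeine". Under Number of Patients to Enroll there are four groups of 20. The baseline visit in Study Data and Outcome Measures includes a case history but does not mention habitual caffeine intake.

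**The concern.** The criterion names one population (people who may be tolerant to caffeine) and tests for another (people who drink coffee above a set amount). Someone who drinks no coffee but takes several teas or energy drinks a day does not meet the bracketed definition. Neither does someone who adds such products to a single daily cup.

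The sponsor's decision to exclude for tolerance already accepts that tolerance matters to the acute response. If habitual users enter by another route, the measured mean change mixes the response of the intended population with a weaker one. A finding of little or no change could then reflect tolerance rather than absence of an effect. Because habitual intake is not recorded, the analysis could not separate the two explanations afterwards.

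**Working it through.** The protocol gives no effect size, standard deviation, power or sample-size derivation, so there is no stated figure to reproduce. Three checks were made.

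**1. Does the test cover the exposure?**
- Sources recognised in Background and Significance: coffee, tea, cocoa, energy drinks, soft drinks, juice, gum, sweets.
- Sources counted in Exclusion Criteria: coffee.
- Limit or record of the remaining sources elsewhere in the protocol: none.

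**2. What intake passes?** The input is 135–150 mg per regular 236 mL cup (Background and Significance).
- One cup a day, the most the test allows from coffee: about 135–150 mg/day. Other sources: no limit.
- US average of 180 mg/day in cups: 180/150 = 1.20 and 180/135 = 1.33. This is above one cup, but it passes if the caffeine comes from tea or soft drinks.
- Two cups of coffee a day: 2 × 135 = 270 to 2 × 150 = 300 mg/day, which is excluded. The same 270–300 mg/day from energy drinks is not caught by the bracket.

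Two people with equal caffeine intake can therefore be treated differently, depending only on its source.

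**3. Direction of the effect on the result.** Let Δ be the mean change in the intended population, f the share of tolerant participants, and b the fraction of the response they lose. The mean change in the enrolled group is

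(1 − f)Δ + f(1 − b)Δ = Δ(1 − fb).

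For any f and b above 0 (and up to 1) this lies nearer zero than Δ. The direction is fixed; the size depends on f and b, and the protocol gives neither.

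*Illustration on assumed values only.* Take f from 10% to 30% (2 to 6 people in a group of 20) and b from 50% to 100%. The shrinkage fb then runs from 0.10 × 0.50 = 5% to 0.30 × 1.00 = 30%. Suppose also that a group of 20 had 80% power for its within-group change at two-sided 5% with no tolerant participants. The standardised change is then d = (1.960 + 0.842)/√20 = 0.626, and power is Φ(d(1 − fb)√20 − 1.960), with the standard deviation held fixed:

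| f | b = 50% | b = 100% |
|---|---|---|
| 10% | 76% | 71% |
| 20% | 71% | 61% |
| 30% | 66% | 50% |

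The table shows how sensitive a group of this size would be. It does not estimate what happens in this trial.

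**The case against.** Several counter-arguments have force.

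- **The lead-in is general.** It speaks of possible tolerance to caffeine, so an investigator taking a case history could exclude a heavy energy-drink user by judgement. This stands: such people *can* be enrolled, and nothing shows that they are. But the bracket is the only test supplied, and a literal reader would admit them.
- **Coffee is a reasoned proxy.** The Background and Significance section says why caffeine is associated mainly with coffee. This stands, and it probably limits how many participants are affected. It does not close the gap for those whose caffeine comes from elsewhere.
- **Participants are their own controls.** Each is measured before the tablet and one and two hours after it, so habitual intake does not confound the within-person change. That is correct. Tolerance acts here by modifying the response: the cost is lost sensitivity and an understated effect, not a spurious one.
- **The size is unknown.** This also stands. The protocol does not say at what intake tolerance begins or how complete it is, and the 180 mg/day average says nothing about how many people pass the screen on non-coffee caffeine.
- **The statistical analysis plan could deal with it.** Eligibility is fixed in the protocol, and no analysis can recover intake that was never recorded.

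A reader might also object that the cup has no size, or that the rule would catch drinkers of decaffeinated coffee. Neither adds much. Background and Significance describes a regular cup as 236 mL, and the stated purpose makes it unlikely that anyone would apply the rule to decaffeinated coffee.

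**Conclusion.** The point holds as a modest, cheaply corrected weakness in one eligibility line. The criterion and the background section do not agree on what counts as caffeine exposure. Regular users of non-coffee sources can be enrolled, and any tolerance they have would bias the acute change toward zero. This rests on the sponsor's own premise that tolerance weakens the response, and on the bracket being applied as written.

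A reader might infer three stronger conclusions that the documents do not support:

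- **The effect will be diluted by some stated percentage.** Any such figure comes from assumed values of f and b, as above.
- **The comparison by diagnosis planned under Statistical Analysis is distorted.** That would require non-coffee intake to differ between groups, and nothing in the protocol indicates that it does.
- **The protocol already sets a limit of 150 mg/day.** It sets no limit in mg; 150 is only the upper end of its range for one cup.

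**What to change.** - **Criterion.** Reconcile Exclusion Criteria with Background and Significance by defining the exclusion on total habitual caffeine from all sources. Express it as the equivalent of the one regular cup the protocol already uses (236 mL, about 135–150 mg). The exact threshold is the sponsor's decision and should be written into the criterion.
- **Record.** Add a short all-source intake checklist at screening and record the estimate in mg/day. Intake can then be described by group and used in a sensitivity analysis of the acute change.
- **Conclusion.** Word the conclusion as applying to people at or below the chosen intake.

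The cost is a one-line amendment and a brief checklist. Some candidates who would now pass will be excluded, so recruitment may be slightly slower.

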#### **Number of Patients to Enroll**

- 20 patients with early stage primary open angle glaucoma
- 20 patients with moderate stage primary angle glaucoma

- 20 patients with advanced stage primary angle glaucoma
- 20 healthy subjects without glaucoma

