### **Study Data and Outcome Measures**

All included patients will undergo a baseline examination involving case history. Measurement of best corrected visual acuity, visual field examination, corneal pachymetry, Axial length, and examination of the anterior and posterior segments of the eye.

The IOP, systolic and diastolic blood pressure, and heart rate will be checked before, and one hour and two hours after caffeine ingestion. The severity of glaucomatous damage was classified into early, moderate and severe stage according to Hodapp-Parrish-Anderson criteria.

Macular and peripapillary blood flow index, vessel density, areas of capillary dropout or non-perfusion detected by OCT angiography will be assessed before, one hour and two hours after the ingestion of caffeine tablet.

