### **Procedures Involved**

Qualifying patients presenting to the Wills Eye Hospital Glaucoma Service will be asked for enrollment. Informed consent will be obtained from all participants. Subjects will undergo a comprehensive eye examination including Humphrey visual field and ocular biometry in both eyes. Scans will be obtained with the Avanti AngioVue HD OCTA (Optovue, Inc, Fremont, CA, USA), before and, one hour and two hours after a 200 mg caffeine tablet ingestion. All eyes will undergo imaging using the standard 4.5 mm HD Disc

scan protocol and the 6mm HD Retina scan protocol. In addition, a regular ONH structural scan (along with a 3D-Disc baseline scan) and a regular GCC structural scan will be acquired which provide comparison to normative database of the device to characterize the RNFL and GCC thickness status of the study eyes. Arterial blood pressure, heart rate and IOP will also be measured before and, one and two hours after the 200 mg caffeine tablet ingestion.

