## **Data analysis**

### OCT Analysis

Acceptable images should have clear and sharp focus artifacts free (e.g., motion lines), without motion artifact (identified by horizontal misalignment of vessel segments on en face images), and Scan Quality of 6 or higher. The scans will be evaluated for vessel density, vessel length per unit area, flow index, foveal avascular zone area. Capillary dropout will also be recorded, if present.

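### Does the protocol need a rule for which eye sets a patient's glaucoma stage when the two eyes differ?

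*Protocol*

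**What the plan says.** The Protocol section Number of Patients to Enroll sets four quotas of 20: early, moderate and advanced glaucoma, and healthy subjects. The unit is the person, as in "20 patients with early stage primary open angle glaucoma". Inclusion is also at the level of the person, with no requirement on either eye.

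The measurements are taken by eye. Under Procedures Involved, "Subjects will undergo a comprehensive eye examination including Humphrey visual field and ocular biometry in both eyes". The scanning rule is equally broad: "All eyes will undergo imaging using the standard 4.5 mm HD Disc". The same paragraph says that the structural scans serve "to characterize the RNFL and GCC thickness status of the study eyes", which is the only use of that term. Under OCT Analysis, "The scans will be evaluated for vessel density, vessel length per unit area, flow index, foveal avascular zone area", with no limit to one eye.

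On staging, Study Data and Outcome Measures says only: "The severity of glaucomatous damage was classified into early, moderate and severe stage according to Hodapp-Parrish-Anderson criteria". It does not name the worse eye, the better eye or a chosen eye. Some exclusions describe an eye rather than a person, for example "Corneal scarring in central 4 mm" and "Refractive spherical diopter >5 or cylinder > 3". The section Statistical Analysis announces a comparison of blood flow by diagnosis, as a subgroup analysis.

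**The concern.** Glaucoma can be more advanced in one eye than in the other, and nothing in the protocol requires the two eyes to share a stage or the fellow eye to be affected at all. A patient with one early and one advanced eye therefore fits two quotas, and two recruiters who both follow the text could file that patient differently. Quotas are filled at enrolment, so a SAP written later cannot undo who filled which place.

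If both eyes were then summarised under the patient's label, eyes of one stage would sit in another stage's group and could weaken the comparison by diagnosis. If the two eyes were also treated as independent observations, standard errors would be too small. The eye-specific exclusions raise a similar question: does one affected eye exclude the person, or only that eye?

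**Working it through.** The protocol states no alpha, power, effect size, standard deviation, between-eye correlation or discordance rate, so there is no sample-size figure to reproduce. What can be checked is the counting, and what would follow under stated assumptions.

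1. **Counts.** 4 × 20 = 80 people. With two eyes each there are up to 160 eyes, or 40 per group. Glaucoma patients number 3 × 20 = 60.

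2. **Patients with two possible quotas.** Let d be the share of glaucoma patients whose eyes differ in stage (assumed 0.1 to 0.5). Affected patients are 20d = 2 to 10 per stage and 60d = 6 to 30 overall.

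3. **Dilution, only if both eyes carry the patient's label.** The share of eyes under the wrong stage is d/2, which is 0.05 to 0.25. If every misfiled eye belongs to the adjacent group, the retained difference between two adjacent groups is 1 − d/2 when one group is affected (0.95 to 0.75) and 1 − d when both are (0.90 to 0.50). That is an unfavourable pattern, not the general one. Put the stage means at equal steps (healthy −1, early 0, moderate 1, advanced 2) and take d = 0.5:
   - Patients labelled by the worse eye, each discordant fellow eye one step milder: early = 0.75 × 0 + 0.25 × (−1) = −0.25, and moderate = 0.75 × 1 + 0.25 × 0 = 0.75. The difference is 1.00, so nothing is lost between these stages. Healthy against early becomes −0.25 − (−1) = 0.75, so that contrast keeps 75%.
   - Early patients' discordant eyes moderate, moderate patients' discordant eyes split evenly between early and advanced: early = 0.25 × 1 = 0.25, and moderate = 0.75 × 1 + 0.125 × 0 + 0.125 × 2 = 1.00. The difference is 0.75.
   - Each eye analysed under its own stage: no eye is misfiled and the question does not arise.

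4. **Error rate, only if two eyes are taken as independent.** With between-eye correlation r of the change (assumed), the true level of a nominal 5% test of change within a group is 2 × (1 − Φ(1.96/√(1 + r))): 8.6% at r = 0.3, 11.0% at 0.5 and 15.5% at 0.9. The protocol does not say that eyes will be analysed this way.

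5. **What can be recovered after enrolment.** Fields are taken in both eyes. Assuming stage is read from the field, every eye's stage can be assigned from data the protocol already collects. The only thing that cannot be restored is exactly 20 patients per stage, and no calculation in the protocol rests on that number.

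**The case for a change.** The strongest case for a change is that assigning a patient to a quota is an act of enrolment, the enrolment rules are in this document, and one sentence would settle the matter at no cost in measurements. It is true that the text is silent on which eye decides, and that a SAP cannot choose afterwards who filled which place. That much stands.

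It does not carry the consequences attached to it. In a randomised trial stratified at entry, a wrong stratum is built into the allocation. Here stage is a measured baseline attribute in a single-treatment study, and regrouping by the stage of the eye analysed, under a rule fixed before analysis, is legitimate. The Objectives and Hypothesis concern change after caffeine in glaucoma patients and in healthy subjects. The early, moderate and advanced labels do not alter a before-and-after change taken over all glaucoma patients.

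The other strands are weaker. The plural reference to study eyes, directly after a rule to scan all eyes, reads naturally as the scanned eyes. The exclusion list governs who enters and mixes ocular items with items such as pregnancy and cardiac disease, so its ordinary meaning is that a listed condition excludes the person.

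Nor is there one obvious rule to impose. The worse eye, a randomly drawn eye, or both eyes staged separately are all defensible. Drawing one eye could turn a patient away because the drawn eye's quota is full. Against a mean of two same-stage eyes it would also raise standard errors by the factor √(2/(1 + r)): 1.03 at r = 0.9 and 1.24 at r = 0.3.

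**Conclusion.** No change to the plan follows. This is a gap that the study team can fill sensibly, using fields that are already taken in both eyes. No stated rule or number in the protocol gives a wrong result.

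The size cannot be fixed from the document. Under an assumed 10% to 50% discordance, 6 to 30 of 60 glaucoma patients would have two possible quotas. Even then the early-to-moderate difference could be kept in full or fall to half, depending on a labelling practice the protocol does not state, and it is unaffected if each eye is analysed under its own stage. The inflated error rates apply only if eyes are treated as independent, which the protocol does not propose. The unit of analysis and the handling of paired eyes commonly belong in a SAP. What remains is that the per-stage counts may depart from 20, which affects no stated calculation. Naming the deciding eye would be a helpful clarification, but the planned analyses do not depend on it.

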### **Study Timeline**

Patient enrollment will begin after IRB approval. We plan to complete enrollment and data acquisition within 1 year of IRB approval.

### **Study Data and Outcome Measures**

All included patients will undergo a baseline examination involving case history. Measurement of best corrected visual acuity, visual field examination, corneal pachymetry, Axial length, and examination of the anterior and posterior segments of the eye.

The IOP, systolic and diastolic blood pressure, and heart rate will be checked before, and one hour and two hours after caffeine ingestion. The severity of glaucomatous damage was classified into early, moderate and severe stage according to Hodapp-Parrish-Anderson criteria.

Macular and peripapillary blood flow index, vessel density, areas of capillary dropout or non-perfusion detected by OCT angiography will be assessed before, one hour and two hours after the ingestion of caffeine tablet.

### **Procedures Involved**

Qualifying patients presenting to the Wills Eye Hospital Glaucoma Service will be asked for enrollment. Informed consent will be obtained from all participants. Subjects will undergo a comprehensive eye examination including Humphrey visual field and ocular biometry in both eyes. Scans will be obtained with the Avanti AngioVue HD OCTA (Optovue, Inc, Fremont, CA, USA), before and, one hour and two hours after a 200 mg caffeine tablet ingestion. All eyes will undergo imaging using the standard 4.5 mm HD Disc

scan protocol and the 6mm HD Retina scan protocol. In addition, a regular ONH structural scan (along with a 3D-Disc baseline scan) and a regular GCC structural scan will be acquired which provide comparison to normative database of the device to characterize the RNFL and GCC thickness status of the study eyes. Arterial blood pressure, heart rate and IOP will also be measured before and, one and two hours after the 200 mg caffeine tablet ingestion.

